Once informed consent is obtained, we will collect data on all subjects' demographics, co-morbidities, surgical history, pertinent microbiology results, and all concomitant medications using standardized forms. For exclusion criteria e) and f) regarding cytopenias and liver function, CBC/CMPs from the past 14 days will be evaluated through a medical chart review. Note that if a CBC has not been performed within the past 14 days, a CBC will be performed on the day of enrollment prior to any study drug being administered to ensure the patient does not meet exclusion criteria (see exclusion criteria e) and f)).

Upon confirmation of eligibility, the study coordinators will call the pharmacy, which will be the LA BioMed Investigational Drug Service (IDS). The research pharmacists at the LABioMed Investigational Drug Service (IDS) will dispense the medication to the subject. Subjects will be given detailed verbal instructions on the use of the medication in either English or Spanish as preferred by the subject. The subject will be given a medication diary and asked to record the time of day when they take each pill as well as any side effects or comments. The subject will be given a small card to keep on their person with information about the study and study staff and emergency contact information. The study staff will answer any questions that the subject has at this time and will encourage the subject to contact the study staff with any future questions.

The subject will present to the Clinical and Translational Research Unit (CTR), the clinical site of the UCLA Clinical and Translational Science Institute (CTSI) on the Harbor-UCLA campus for follow up visits. These follow up visits will occur at week 1, week 2, week 3, week 4, week 5, week 6, week 7, week 8, week 9, week 10, week 11, week 12 and week 13. All subjects will return for follow up visits on weeks 1 – 5 and 12, and subjects still taking the study drug after week 5 will continue to return for weekly follow up visits until they complete the course or until they reach 12 weeks. Once subjects complete the course of the study drug, they will return for one additional weekly follow up visit (e.g. if a patient completes the study drug at 7 weeks, they will return for visits on weeks 1-8 and week 12). If subjects take the study drug for 12 weeks, they will return for a final follow up visit on week 13.

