At each follow up visit, CBC and CMP (comprehensive chemistry panel including liver function tests) will be collected via a blood draw. This blood sample will be sent to Quest Diagnostics by the

PROTOCOL TITLE: *Tolerability, Safety, and Efficacy of Tedizolid as Oral Treatment for Bone and Joint Infection*

Revised: 8/10/18 Version 1.6

CTSI/CTRU, an outside laboratory that is contracted with the CTSI/CTRU to process blood samples. Additionally, standardized surveys (See Data Collection Fields V 1.0, Neuropathy Scale V 1.0, attached) will be administered about drug side effects and tolerability, and adverse events will be measured using the Medical Dictionary for Regulatory Activities Terminology (MedDRA) version 18.1 (or the most current version). At these follow up visits, we will also record data points relevant to defining the efficacy of the treatment, such as the duration of the antibiotic treatment, any unplanned surgical procedures prompted by inadequate infection control, recurrence of signs or symptoms of bone and joint infection, and any other relevant comments or observations from the subject. The subject will also be asked to bring their study drug medication bottle and medication diary in order to assess compliance. If a subject suspects pregnancy during a follow up visit, they will be given a pregnancy test and the study team will track their reported menstrual cycle. If the subject does become pregnant, they will be discontinued from the study drug. Study staff will follow and collect data on the course of the pregnancy and the health of the child for at least 6-8 weeks after delivery.

Patients with evidence of myelosuppression will continue to have weekly CBCs performed until resolution of the myelosuppression.

Subjects who are concurrently taking serotonergic agents while receiving the study drug will be monitored for signs and symptoms of serotonin syndrome at each scheduled follow-up visit. Symptoms of serotonin syndrome include agitation or restlessness, confusion, rapid heartbeat and high blood pressure, dilated (big) pupils, loss of muscle coordination or twitching muscles, muscle rigidity (stiffness), heavy sweating, diarrhea, headache, shivering and goose bumps.

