The study staff and study investigators will review the data.

Study staff will review all recorded data at regular monthly intervals with the primary investigator, [name]. If [name] is not available, the co-investigator, [name], will review the monthly data.

The Data Safety Monitor ([name]) will review safety data including labs, vital signs, results of peripheral neuropathy scales, and all reported adverse events, side effects, complications, or other patient feedback. This review will occur on a quarterly basis, with the first review happening after either three months or after 10 patients have been enrolled, whichever comes first.

The frequency or periodicity of review of cumulative data.

Cumulative safety data will be reviewed by the study staff and study investigators as it becomes available.

The statistical tests for analyzing the safety data to determine whether harm is occurring.

We will perform reviews once per quarter of the cumulative side effects. A summary of these safety data including labs, vital signs, results of peripheral neuropathy scales, and all reported adverse events, side effects, complications, or other patient feedback will be shared with the study's Data Safety Monitor, [name]. If there is a statistically significant side effects, the Principal Investigator and/or the Data and Safety Monitor for the study, will consider reporting this to the IRB if the side effects are felt to put subjects at harm. Any serious adverse events that pose a risk to the subject or others and are deemed unexpected and possibly or probably related to the study will be reported to the IRB within 24 hours of the study staff being aware of this event, in accordance with HRP-214.

- *Any conditions that trigger an immediate suspension of the research.*

If, in the belief of the Principal Investigator or the Data and Safety Monitor, there are events that put subjects at undue risk, due to either cumulative or individual events outlined above, the study will be immediately suspended.

I) Withdrawal of Subjects*

Describe anticipated circumstances under which subjects will be withdrawn from the research without their consent.

Subjects will be withdrawn from the study without their consent if the principal investigator determines this is necessary to protect the safety of the subject.

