Additionally, subjects may be withdrawn in the following circumstances development of significant cytopenias and liver function abnormalities, symptoms of neuropathy, gastrointestinal intolerance, or, in the opinion of the investigator, any new severe signs or symptoms that may be related to the study drug.

PROTOCOL TITLE: *Tolerability, Safety, and Efficacy of Tedizolid as Oral Treatment for Bone and Joint Infection*

Revised: 8/10/18 Version 1.6

If a subject becomes pregnant during the study, they will be discontinued from the study drug. Study staff will follow and collect data on the course of the pregnancy and the health of the child for at least 6-8 weeks after delivery.

Describe any procedures for orderly termination.

Termination of the study will occur based on the primary investigators judgment. Subjects will be provided referrals for their medical conditions, if needed.

Describe procedures that will be followed when subjects withdraw from the research, including partial withdrawal from procedures with continued data collection.

Subjects who withdraw from the study will be asked to notify the study team. No further visits will be required. Additionally, if a subject withdraws from the study, a member of the study team will contact their primary treatment physician and/or infectious disease consultant to ensure that the patient is given antibiotic therapy immediately upon discontinuation of study drug.

10) Risks to Subjects*

List the reasonably foreseeable risks, discomforts, hazards, or inconveniences to the subjects related the subjects' participation in the research. Include as may be useful for the HSC's consideration, describe the probability, magnitude, duration, and reversibility of the risks. Consider physical, psychological, social, legal, and economic risks.

According to the package insert for tedizolid (Sivextro), adverse reactions were evaluated for 1050 patients treated with tedizolid (200 mg oral/intravenous once daily for 6 days) in two Phase 2 and two Phase 3 ABSSSI (acute bacterial skin and soft structure infection) clinical trials. The median age of patients treated with tedizolid (200 mg oral/intravenous once daily for 6 days) in the Phase 2 and Phase 3 ABSSSI trials was 42 years, ranging between 17 and 86 years old. Patients treated with tedizolid (200 mg oral/intravenous once daily for 6 days) were predominantly male (65%) and white (82%).

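### No rule assures chemistry-panel or neuropathy-scale follow-up for subjects whom the investigator withdraws for toxicity

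*Combined protocol and SAP*

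**What the plan says.** Section 9(l) first answers a prompt about removing subjects from the research without their consent. The general rule is: "Subjects will be withdrawn from the study without their consent if the principal investigator determines this is necessary to protect the safety of the subject". It then adds that "subjects may be withdrawn in the following circumstances development of significant cytopenias and liver function abnormalities, symptoms of neuropathy, gastrointestinal intolerance", together with any new severe sign or symptom that the investigator thinks may be drug-related.

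Pregnancy is worded differently: "If a subject becomes pregnant during the study, they will be discontinued from the study drug", and data collection then continues until at least 6 to 8 weeks after delivery.

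The next prompt asks for withdrawal procedures, "including partial withdrawal from procedures with continued data collection". The answer is "Subjects who withdraw from the study will be asked to notify the study team. No further visits will be required", followed by an undertaking to contact the treating physician so that replacement antibiotics start at once.

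Section 9(g) sets the schedule: "All subjects will return for follow up visits on weeks 1 – 5 and 12", plus weekly visits while on drug and one extra weekly visit for those who complete the course. It also says "At each follow up visit, CBC and CMP (comprehensive chemistry panel including liver function tests) will be collected via a blood draw", and gives the side-effect surveys and neuropathy scale at the same visits. For one toxicity there is a specific rule: "Patients with evidence of myelosuppression will continue to have weekly CBCs performed until resolution of the myelosuppression".

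**The concern.** Section 4 sets out to quantify tolerability and safety, and names hematologic and neurologic toxicity as a focus. Section 5 warns that neurologic toxicity with linezolid, the other marketed drug in the class, may not reverse. Section 10 states that use for 4 to 12 weeks has not been studied. Whether a liver abnormality or neuropathy settles after tedizolid is stopped is therefore useful information, and it can come only from subjects who develop the problem.

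Those are the subjects whom section 9(l) allows to leave with no stated assessment afterwards. The event that prompted withdrawal would be on record, but its recovery or persistence might not be. For gastrointestinal intolerance the loss is smaller, mainly the later tolerability surveys.

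**Working it through.** **Does any other text close the gap?**

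- *The all-subjects schedule in 9(g).* It covers a subject who stops drug and stays in the study. It does not say that it survives withdrawal.
- *The extra weekly visit in 9(g).* It is written for subjects who complete the course, so an early stopper cannot count on it.
- *Weekly blood counts for myelosuppression.* These cover cytopenia well, and need only a statement that they continue off drug. They include neither the chemistry panel nor the neuropathy scale.
- *The three-month phone survey.* This is self-report. No laboratory test or neuropathy scale is stated for it, and the plan does not say whether it is kept after withdrawal.
- *Laboratory reports from the medical record (9(g)).* Collection after withdrawal is not stated, and the neuropathy scale is given at study visits.
- *Safety collection in 9(k).* It runs through the medication diary, the same visits and the phone call.

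**What a subject who stays in the study would get**

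Payments come from 9(a) and 9(g): $30, $35, $40, $40, $45 and $45 for weeks 1 to 6, and $50 each for weeks 7 to 13. The plan's range reproduces:

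- Weeks 1 to 5 sum to 30 + 35 + 40 + 40 + 45 = 190.
- Minimum: 190 + 50 (week 12) = $240.
- Maximum: 190 + 45 + 7 × 50 = $585.

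Let s be the last week on drug in an early stop. On a strict reading, off-drug visits are those of weeks 1 to 5 and 12 that fall after s. The fix below adds week s + 1 where it is not already scheduled.

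| s | Off-drug visits, strict reading | With the fix | Total payment with the fix |
|---|---|---|---|
| 1 | 5 (weeks 2, 3, 4, 5, 12) | 5 | $240 |
| 2 | 4 | 4 | $240 |
| 3 | 3 | 3 | $240 |
| 4 | 2 (weeks 5, 12) | 2 | $240 |
| 5 | 1 (week 12) | 2 (weeks 6, 12) | 190 + 45 + 50 = $285 |
| 6 to 10 | 1 (week 12) | 2 (weeks s + 1, 12) | $335, rising by $50 a week to $535 |
| 11 | 1 (week 12) | 1 | 190 + 45 + 6 × 50 = $535 |

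For a subject withdrawn by the investigator, the assured number is 0 if the no-visits sentence applies. If that sentence covers self-withdrawal only, the number is unstated.

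**How many subjects?**

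The documents give event rates from 6-day courses only (section 10). Applied to the approximately 55 enrolled (9(c)):

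- Peripheral neuropathy, 1.2%: 0.012 × 55 = 0.66 expected; chance of at least one, 1 − 0.988^55 = 0.485.
- Raised transaminases, under 2%: fewer than 0.02 × 55 = 1.1 expected.
- Discontinuation for any adverse reaction, 3/662: (3/662) × 55 = 0.25 expected; chance of at least one, 1 − (1 − 3/662)^55 = 0.22.

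None of these is a withdrawal rate, and rates over 4 to 12 weeks are not given. They indicate small numbers but do not size the gap.

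**The case against.** The strongest reply is that the no-visits sentence speaks of subjects who withdraw and asks them to notify the team. A subject removed by the investigator has no need to do that. The sentence also releases the subject from an obligation; it does not bar follow-up. The toxicity sentence is permissive, and section 9(l) uses withdrawal and stopping drug loosely. Nothing prevents an investigator from stopping drug and keeping the subject on the 9(g) schedule.

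All of that stands. A reader might infer that the plan requires subjects with toxicity to be removed and forbids seeing them again; the documents do not support that. They leave follow-up after investigator withdrawal unstated, and the prompt about continued data collection unanswered.

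It is also fair to say that section 9(f) names no recovery or reversibility endpoint, so the plan does not fail an endpoint it set. The loss is of safety information that bears on its stated objective.

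Two further inferences should be resisted. One is that these subjects are left without care. Section 9(l) has the team contact the treating physician, and section 21 passes significant results to primary care providers if clinically indicated. The other is that 49% is the chance of losing a neuropathy outcome. It is the chance of at least one event at a 6-day rate, and not every event would lead to withdrawal.

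**Conclusion.** The concern holds in limited form. For subjects whom the investigator withdraws for liver abnormality, neuropathy symptoms or gastrointestinal intolerance, no text assures a later chemistry panel, neuropathy scale or tolerability survey. Cytopenia is largely covered, pregnancy is handled correctly, and a subject who only stops drug keeps between 1 and 5 scheduled visits.

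The number affected is unknown and probably small. In a single-arm study of about 55 people, however, even one unrecorded outcome of a neuropathy would be a real loss. The amendment is worth making because it is cheap and because off-drug findings may not be recoverable later.

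This rests on the protocol text alone; the attached data forms were not available. It makes no claim about which subjects enter the denominators, which is a separate question.

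**What to change.** In section 9(l), make the listed toxicities reasons to stop study drug by default, following the model already used for pregnancy. Then add a paragraph along these lines:

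*A subject who stops study drug early stays in follow-up: all remaining visits at weeks 1 to 5 and 12, plus a visit one week after the last dose if none is scheduled, each with CBC, CMP and neuropathy scale, and the three-month call. Weekly CBCs for myelosuppression continue off drug until resolution. Exceptions are subjects who withdraw consent to follow-up and those for whom the investigator judges study follow-up itself unsafe. Liver abnormality or neuropathy unresolved at the last study visit is handed over to the treating physician.*

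Limit the no-visits sentence to subjects who withdraw consent to follow-up. Keep the investigator's general power to withdraw a subject from the study for safety, and change nothing about when drug is stopped.

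The cost is a short edit and, per affected subject, 1 to 5 visits with blood draws that would otherwise not be assured. Measured against no visits after the stop, added payment runs from $50 (stop at week 11: 535 − 485) to $210 (stop at week 1: 240 − 30). Laboratory cost is not given. The limitation is that chemistry and neuropathy assessments still end at week 12. Toxicity that appears late gets only short off-drug observation, a single visit one week later for a stop at week 11, before hand-over.
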